#### 4.4.9 Modified Severity Weighted Assessment Tool (mSWAT)

The mSWAT is designed to quantify the disease burden associated with CTCL and is based on an estimate of the percent total area of skin involved based on the body surface area (BSA). The types of lesions are weighted by the lesion characteristic (patch, plaque, or tumor) as shown in [Table 5](#). The mSWAT score will be assessed at Baseline and at End of Study.

**Table 5: Modified Severity Weighted Assessment Tool (mSWAT)**

Body Region	% BSA a in Body	Assessment of Involvement in Patient's Skin		
		Region	Patch b	Plaque c
Head	7%			
Neck	2%			
Anterior trunk	13%			
Arms	8%			
Forearms	6%			
Hands	5%			
Posterior trunk	13%			
Buttocks	5%			
Thighs	19%			
Legs	14%			
Feet	7%			
Groin	1%			
Weighting Factor		x1	x2	x4

Body Region	% BSA a in Body	Assessment of Involvement in Patient's Skin		
		Region	Patch b	Plaque c
Subtotal lesion BSA x weighting factor				

a BSA=body surface area

b Any size lesion without induration or significant elevation above the surrounding uninvolved skin; poikiloderma may be present

c Any size lesion that is elevated or indurated; crusting, ulceration, or poikiloderma may be present.

d Any solid or nodular lesion>1 cm in diameter with evidence of deep infiltration in the skin and/or vertical growth.

#### 4.4.10 Skin Reaction Safety Grading

Approximately 5 to 10 minutes before and after the completion of light therapy, treated lesions will be graded for erythema with the worst, best, and “average” scores recorded. The reaction will be graded using the definitions in [Table 6](#).

**Table 6: Phototoxicity/Erythema Score**

Toxicity Grade: Erythema and/or edema	Severity
Grade 0	No apparent reaction
Grade I	Mild
Grade II	Moderate
Grade III	Severe with edema
Grade IV	Life-threatening with vesiculation

## 5. STATISTICAL CONSIDERATIONS

This is an open-label, uncontrolled interventional trial. Data will be summarized as counts for categorical variables and the number, mean, standard deviation, median and ranges will be presented for continuous variables.

### 5.1. Sample Size Calculation

The sample size used for this trial is arbitrary and not based on power calculations.

### 5.2. Analysis Populations

The analysis population is the Intent-to-Treat (ITT) population defined as all patients enrolled. All patients enrolled will be reported for all periods in which they have data available.

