## 5 POPULATION

### 5.1 Number of Subjects

Approximately 6 subjects will be enrolled.

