#### **5.4 Premature Discontinuation**

Patients have the right to withdraw from this trial at any time (as described in the informed consent document) without prejudice to further care. An investigator may withdraw a patient from the study at any time for any of the following reasons:

- The patient withdraws his/her consent or refuses follow-up evaluations.
- The patient is lost to follow-up and will not attend further study visits.
- The investigator determines that further participation would be detrimental to the patient's health or well-being.
- The patient fails to comply with the study requirements so as to cause harm to self or seriously interfere with the validity of the study results.
- The female patient becomes pregnant during the treatment period. In this case, treatment should be halted and the patient followed until the end of the pregnancy. If a child is born, the infant should be followed through at least 6 months of age.
  - At the discretion of the site investigator if he/she feels that it is in the best medical interest of the patient.

Patients withdrawn from the study will have as many of the trial assessments completed as the patient permits including blood tests and lesion evaluations.

Patients withdrawn from the study may be replaced up to a total of 8 subjects provided that both the PI and the Soligenix Medical Monitor agree that the reasons for withdrawal do not suggest a change in the risk assessment of the HyBryte therapy.

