## 2. STUDY OBJECTIVES

### 2.1. Primary Objectives

- Assess any electrocardiogram (ECG) changes during standard HyBryte photodynamic therapy.
- Assess the systemic blood levels of hypericin during standard HyBryte photodynamic therapy.

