#### 6.1.1 Analysis of Central Tendency

The mean and median response at Baseline and at each subsequent timepoint for each parameter will be assessed. Changes in response will be tracked and compared. The clinical meaningfulness of any alterations will be assessed.

Individual changes in each parameter will also be plotted and compared for evidence of trends.

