### 6.2. Hypericin blood concentrations

Hypericin blood calculations will be summarized as the mean, standard deviation and range of blood concentrations for each timepoint. A regression between cumulative drug application and measured blood concentration per visit (average result where samples were collected before and after light collection) will be conducted excluding the End of Study sample, if at least 50% of samples had detectable levels of circulating hypericin.

Changes in blood concentration over time will be described for each individual subject to assess the potential for accumulation.

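### The hypericin and ECG timepoint means take in every enrolled patient with data, with no rule for samples where the preceding drug application was not made

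*SAP*

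**What the plan says.** SAP 2.1 states one primary objective as "Assess the systemic blood levels of hypericin during standard HyBryte photodynamic therapy"; the other asks about ECG changes over the same therapy.

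SAP 5.2 defines a single population: "The analysis population is the Intent-to-Treat (ITT) population defined as all patients enrolled". It adds: "All patients enrolled will be reported for all periods in which they have data available". A per-protocol population appears in the SAP abbreviation list but is never defined.

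SAP 6.2 has hypericin "summarized as the mean, standard deviation and range of blood concentrations for each timepoint", followed by a regression on cumulative drug applied, run only if at least half the samples are detectable. For ECGs, SAP 6.1.1 says: "The mean and median response at Baseline and at each subsequent timepoint for each parameter will be assessed". Neither section makes a patient's inclusion at a timepoint depend on a recent application.

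Protocol 5.4 foresees data after a patient leaves: "Patients withdrawn from the study will have as many of the trial assessments completed as the patient permits including blood tests and lesion evaluations". On numbers, protocol 5.1 says "Approximately 6 subjects will be enrolled", and protocol 5.4 adds "Patients withdrawn from the study may be replaced up to a total of 8 subjects".

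The protocol does collect what is needed to tell whether drug was applied. Staining is inspected at each light session. Jars are weighed at the light sessions up to Week 8 Session 1, and before and after the supervised Week 8 Session 2 application (protocol 5.3.3 to 5.3.9). No analysis rule uses these records to qualify a sample.

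**The concern.** An all-enrolled population protects a randomised comparison. This trial has none. For a question about exposure while on treatment, the same rule can mix samples taken after an application with samples taken from a patient who did not apply drug.

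Where that happens, the hypericin and ECG means shift toward the finding that the study is set up to confirm, namely low systemic exposure without ECG change. With 6 patients, each is a sixth of every timepoint mean. Two further outputs are touched. Undetectable off-drug samples make the 50% detectability condition for the regression harder to meet. The regression's covariate, cumulative drug, does not fall when a patient stops, so it cannot identify such a sample.

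**Working it through.** There is no plan figure to reproduce: SAP 5.1 calls the sample size arbitrary. The check is a weighted mean.

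**Inputs from the documents**
- N = 6 planned (protocol 5.1), up to 8 with replacement (protocol 5.4).
- Assay detection level 0.05 ng/mL (protocol 1.2).
- A result reported as below X is analysed as X (SAP 5.4). I take X = 0.05 ng/mL.

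**Assumptions**
- On-drug level c of 0.1, 0.3 or 0.5 ng/mL. The two higher values are the upper figures for minipigs with and without light (protocol, Figure 1 text); no human on-drug value is given.
- k patients off drug at the timepoint: 1 of 6, or 2 of 8.
- Off-drug patients are undetectable and show no ECG change.

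**Hypericin mean** = [(N − k) × c + k × 0.05] / N

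| k of N | c (ng/mL) | Mean (ng/mL) | Change |
|---|---|---|---|
| 1 of 6 | 0.1 | (5 × 0.1 + 0.05)/6 = 0.0917 | −8.3% |
| 1 of 6 | 0.3 | (5 × 0.3 + 0.05)/6 = 0.2583 | −13.9% |
| 1 of 6 | 0.5 | (5 × 0.5 + 0.05)/6 = 0.4250 | −15.0% |
| 2 of 8 | 0.1 | (6 × 0.1 + 0.10)/8 = 0.0875 | −12.5% |
| 2 of 8 | 0.3 | (6 × 0.3 + 0.10)/8 = 0.2375 | −20.8% |
| 2 of 8 | 0.5 | (6 × 0.5 + 0.10)/8 = 0.3875 | −22.5% |

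With k = 0 the change is zero in every row. Setting undetectable results to zero would give −16.7% (1 of 6) and −25.0% (2 of 8), but that is not the SAP's rule.

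**Residual drug.** One missed application need not mean an undetectable level. Suppose the systemic half-lives in protocol Table 1 (20.2 to 83.7 h) carried over to topical use, and the missed application added 72 to 96 h. The fraction remaining would run from 2^(−96/20.2) = 0.04 to 2^(−72/83.7) = 0.55. At 0.55, and still detectable, one patient of 6 lowers the mean by (1 − 0.55)/6 = 7.5%.

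**Mean ECG change** = d × (N − k)/N. For an assumed on-drug change d = 10 ms:
- 1 of 6: 10 × 5/6 = 8.3 ms.
- 2 of 8: 10 × 6/8 = 7.5 ms.

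The shrinkage is k/N, or one sixth per patient at N = 6. It is less if some drug effect remains.

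**Regression condition.** With one sample per patient, the on-drug detection rate needed to reach 50% overall is 0.5 × N/(N − k):
- 1 of 6: 60%.
- 2 of 8: 66.7%.

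**The case against.** A reader might infer that off-drug patients will be averaged in. The documents do not show that. Treatment is described as up to 16 sessions in protocol 4.1, but the synopsis counts 16 actual treatments, so missed applications are possible rather than planned. The schedule's footnote on light sessions makes the preceding application part of the session, and the Week 4, 6 and 8 light-session samples and ECGs are timed from that session. A patient who stopped in Week 5 has no Week 8 light session, and no rule assigns a later sample to that timepoint. Protocol 5.4 can also be read as describing an exit assessment. The last application is supervised, and staining is checked at every sampled light session. All of this stands, and it makes the effect conditional.

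A reader might also infer that every primary output is biased. That is not so. Adding off-drug patients cannot lower the maximum in the hypericin range or the number of patients over the SAP 6.1.2 limits. Accumulation is to be described subject by subject (SAP 6.2), and ECG changes are plotted individually (SAP 6.1.1). Jar-weight changes are listed (SAP 6.3) and exposures tabulated (SAP 7.4).

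Nor would the broad conclusion on exposure be likely to move. The comparators are the former 5 ng/mL assay limit and systemic peak levels of 30.6 to 6,400 ng/mL (protocol 1.2 and Table 1). The shifts above are fractions of 1 ng/mL.

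Finally, ECG is a safety parameter analysed in all enrolled patients (SAP 5.3 and 7). Moving the whole ECG analysis to an on-treatment set could drop from the main threshold counts a patient who stopped because of an effect. That objection is sound and limits the remedy.

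What the objection leaves in place is the stated rule itself. It governs both sets of timepoint means, sets no application condition, and does not require off-drug samples to be flagged in the individual displays.

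**Conclusion.** The point holds as a conditional weakness in the population rule. If an enrolled patient gives a Week 4, 6 or 8 sample or ECG without the preceding application, the timepoint means understate on-treatment exposure and ECG change. For hypericin the understatement is about 8% to 15% with one undetectable patient of 6 and about 12.5% to 22.5% with two of 8. A mean ECG change loses up to one sixth per off-drug patient at N = 6.

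The hypericin figures rest on assumed on-drug levels of 0.1 to 0.5 ng/mL and on 0.05 ng/mL as the value for undetectable results. The ECG figure assumes no residual effect off drug. The documents support neither a certain bias nor a bias in all outputs. It is still worth settling before database lock, because a later decision on which samples count would be made with the levels in view.

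**What to change.** In SAP 5.2, add a PK-evaluable flag for each patient and timepoint:
- Week 4, 6 and 8 light-session samples and ECGs: the application for that session is documented by the staining check and the jar-weight change. For Week 8 the weights are those taken at the drug application visit.
- Week 8 pre-application sample: the Week 8 Session 1 application is documented in the same way.
- Week 10: the Week 8 Session 2 application is documented.

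Then:
- Use the flagged set for the SAP 6.2 means and regression, including the 50% detectability condition.
- Show the SAP 6.1.1 ECG central-tendency summary on the flagged set beside the all-enrolled summary.
- Keep the SAP 6.1.2 QT/QTc counts and all safety tables on all enrolled patients.
- List unflagged samples individually and give their number at each timepoint.

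The cost is SAP wording and one derived variable from data already collected, with no new visits or procedures. The downside is a smaller n at any timepoint where an application was missed.

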### 5.3. Methodology and Conventions

All safety endpoints will be analyzed using all enrolled patients.

Lab results obtained from the local laboratories, will be used for all safety analyses. All analyses will be performed using SAS® Version 9.4 or higher.

### 5.4. Additional Data Handling Rules and Presentation Specifications

The following general guidelines will apply to all statistical analyses and data presentations:

Baseline is defined as the last available value obtained prior to the first dose of study drug, unless otherwise specified in this SAP.

By default, US conventional units will be used for laboratory value presentations. A set of lab summary tables in International Standard Units (SIU) will also be provided based on tables, listings and figures.

Age is calculated as of date that the informed consent form was signed - age = floor ((date of Informed Consent – birth date+1)/365.25)

All percentages will be rounded to one decimal place and lined up by the decimal place. The percentage will be suppressed when the count is zero.

Any p-values will be rounded to three decimal places and will be presented as ‘<0.001’ if they are less than 0.001 after rounding.

For continuous variables that are recorded as “< X” or “> X”, the value of “X” will be used in the calculation of summary statistics. The original values will be used for the listings.

Decimal points will be presented as follows: N will be presented without decimal, minimum and maximum in same precision as in the database, mean and median in one more decimal than minimum and maximum, and SD in one more decimal than mean and median.

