## 1.2 Pharmacokinetics

Hypericin was initially developed for the systemic treatment of enveloped viral infections including HIV and hepatitis C virus (HCV) and gliomas. Following dosing with either intravenous (iv) or oral (po) routes, the only consistently reported AEs were caused by phototoxicity, the biologic effect that is being exploited and tightly regulated in the topical treatment of CTCL. Minimal blood levels of hypericin were expected to result from low dose topical application of the drug. During the Phase 3 trial, serum blood levels of systemic hypericin were assessed at the end of the third cycle of therapy (after 5-6 weeks of continuous therapy on multiple lesions). Specific serum blood samples were taken approximately 24 hours after the application of the drug, the time when the maximal skin effects were seen. ***Systemic hypericin was not detected in the blood***, indicating levels were  $<5$  ng/mL (lower limit of detection of the bioanalytical method). This study is designed to expand the information about the systemic absorption of hypericin after topical application. Since the systemic levels of hypericin following topical administration were expected to be orders of magnitude lower than that following iv or po administration in which there was no evidence of electrocardiogram (ECG)

changes, minimal ECG monitoring of CTCL patients has been done. Subsequent to completion of the Phase 3 study, the hypericin blood assay was modified to be more sensitive with a detection level of 0.05 ng/mL. Using this improved assay, hypericin levels were measured in a minipig pilot study in which healthy animals were dosed with hypericin every 2 days and treated with ointment only or varying amounts of light treatment. The results of the study are shown in Figure 1.

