## 8.5. Clinical Laboratory Parameters

If the reported value of a clinical laboratory parameter cannot be used in a statistical summary table due to, for example, that a character string is reported for a parameter of the numerical type, coded value needs to be appropriately determined and used in the statistical analyses ([Table 8](#)). However, the actual values as reported in the database will be presented in data listings.

Categorization of laboratory results into low/normal/high group will be done using the laboratory's scaled lower and upper limits of normal value as present in [Table 8](#) and [Table 9](#).

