**Table 8: Example for Coding of Special Character Values for Clinical Laboratory Parameters**

Lab Test	Reported Lab Results (in SI units)	Coded Value for Analysis
Chemistry: ALT	<5	0

Lab Test	Reported Lab Results (in SI units)	Coded Value for Analysis
Chemistry: AST	<5	0
Chemistry: Bilirubin, Total	<2	0

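### SAP 5.4 and Table 8 code below-limit laboratory results in opposite ways, and hypericin has no below-limit rule except the generic one in 5.4, which could flatten the exposure regression

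*SAP*

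**What the plan says.** **General rule.** SAP 5.4 opens with "The following general guidelines will apply to all statistical analyses and data presentations". One of its rules is that, for a continuous result recorded as `<X`, the number X "will be used in the calculation of summary statistics". Listings keep the recorded value.

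**Laboratory rule.** For a laboratory result that is not numeric, SAP 8.5 says a "coded value needs to be appropriately determined and used in the statistical analyses". Table 8, titled "Example for Coding of Special Character Values for Clinical Laboratory Parameters", gives 0 as the "Coded Value for Analysis" for ALT `<5`, AST `<5` and total bilirubin `<2`.

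**Hypericin.** SAP 4.1 makes serial hypericin levels, and their relation to cumulative drug applied, a primary endpoint. SAP 6.2 plans the mean, SD and range at each timepoint and a description of change over time for each subject. It then plans this: "A regression between cumulative drug application and measured blood concentration per visit", using the average where samples were taken both before and after light. The regression "will be conducted excluding the End of Study sample, if at least 50% of samples had detectable levels of circulating hypericin". Section 6.2 says nothing about values below the limit. The limit itself comes from Protocol 1.2: after Phase 3, "the hypericin blood assay was modified to be more sensitive with a detection level of 0.05 ng/mL".

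**The concern.** There are two linked problems.

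1. **Laboratory tests.** An ALT of `<5` is 5 under SAP 5.4 and 0 under Table 8. Two programmers could each follow the SAP and produce different tables.
2. **Hypericin.** Section 5.4 is the only text that could apply. A pre-drug sample, whose drug-derived level is zero, would be summarised as 0.05 ng/mL. A visit with no detectable drug would show a mean of 0.05, which reads like measured exposure. Section 6.2 drops only the End of Study sample, so Baseline, at zero cumulative drug, stays in the regression. Raising that point flattens the slope and makes any accumulation look smaller. For a safety question about accumulation, that is the unfavourable direction.

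**Working it through.** The plan has no figure of its own to reproduce; SAP 5.1 states that the sample size is not based on a power calculation.

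**Laboratory tests.** With 6 patients (Protocol 5.1), one ALT of `<5` coded 5 or 0 moves the mean by 5/6 = 0.83 U/L.

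**Hypericin inputs**
- Limit X = 0.05 ng/mL (Protocol 1.2).
- Treatment twice weekly (SAP 3). Cumulative applications are therefore 0 at Baseline, 8 at Week 4 Session 2, 12 at Week 6 Session 2, 15 before the last application and 16 at the Week 8 light session.
- Assumptions: equal amount per application, and a level rising linearly from 0 to a final level L.
- The documents give no human level from the sensitive assay. The only guide is the minipig study (Protocol, Figure 1): below 0.5 ng/mL without light and below 0.3 ng/mL with light, after 5 or 6 doses. These are upper bounds, so I show a range of L.

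**Leverage of Baseline**
- Mean applications = 51/5 = 10.2.
- Sum of squared deviations = 104.04 + 4.84 + 3.24 + 23.04 + 33.64 = 168.8.
- Leverage = 1/5 + 104.04/168.8 = 0.82.

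**Effect of coding Baseline 0.05 instead of 0**
- Change in slope = 0.05 × (−10.2)/168.8 = −0.0030 ng/mL per application, whatever L is.
- Slope with Baseline at 0 = L/16.
- Relative loss = 0.00302/(L/16).

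| Final level L (ng/mL) | Slope, Baseline 0 | Slope, Baseline 0.05 | Loss |
|---|---|---|---|
| 0.10 | 0.00625 | 0.00323 | 48% |
| 0.20 | 0.01250 | 0.00948 | 24% |
| 0.30 | 0.01875 | 0.01573 | 16% |
| 0.50 | 0.03125 | 0.02823 | 10% |
| 1.0 | 0.06250 | 0.05948 | 5% |

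In these rows only Baseline is below the limit.

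**Other shapes.** If the level is instead constant from Week 4 on, the loss is 0.05/L: 50% at 0.10, 17% at 0.30 and 10% at 0.50.

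**Six patients with the 50% condition applied.** I simulated 4,000 trials per level. The assumptions, none taken from the documents, were log-SDs of 0.5 for amount applied, 0.4 between patients and 0.3 within patient. For typical final levels of 0.08, 0.15, 0.3 and 0.5 ng/mL:
- the regression was run in 52%, 98%, 100% and 100% of trials;
- the median loss of X coding against 0 coding was 33%, 19%, 8% and 5%;
- the X slope was below the 0 slope in every trial that met the condition.

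The direction is therefore stable, and the size depends on the assumptions.

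**Averaged visits.** A before-light level of 0.12 with an after-light `<0.05` averages to (0.12 + 0.05)/2 = 0.085 under X and (0.12 + 0)/2 = 0.06 under 0. Some numeric value has to be chosen before the regression inputs exist.

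**The case against.** **These points stand.**
- A reader might infer that the SAP has two opposing rules for hypericin. It does not. Table 8 is an example limited to clinical laboratory parameters, and hypericin is defined separately as a pharmacokinetic measure (SAP 4.4.2). For hypericin the fault is a missing specific rule beside a generic one.
- A reader might infer that the SAP prescribes a biased regression. The `<X` sentence names only summary statistics. The preamble of 5.4 allows X to be carried into the regression but does not say so.
- The rule applies only to results recorded as `<X`. The documents provided do not show how the laboratory reports undetected hypericin. If it writes BLQ or not detected, no rule applies. The limit is also worded differently in Protocol 1.2 (a detection level of 0.05) and under Figure 1 (an LLOQ below 0.05).
- The 50% condition often stops the regression where the distortion would be worst, although it does not remove the distortion when the regression runs.
- No group change from baseline is planned for hypericin. An all-undetected visit has SD 0 under zero coding too. Medians are already planned (SAP 5; Protocol 10.2). Listings keep the recorded value.
- For showing that mean exposure is low, using X overstates levels, which is cautious.

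**These points do not remove the problem.**
- Overstating the mean is cautious, but the same substitution understates slope and accumulation.
- If 5.4 does not reach the regression, a primary analysis has no below-limit rule and the choice is made after the data are seen.
- For laboratory tests, one can argue that the specific rule overrides the general one. The SAP does not say this, and the `<X` sentence has no exception clause, unlike the Baseline definition in the same section.

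**Conclusion.** The point holds in a conditional form, with medium confidence.

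- **Laboratory tests:** the contradiction is plain and its effect is small, 0.83 U/L in mean ALT for one `<5` result in 6 patients.
- **Hypericin summaries:** if undetected samples are recorded as `<0.05`, 5.4 reports pre-drug Baseline as 0.05 ng/mL.
- **Hypericin regression:** if X is also carried into 6.2, the slope falls by about 48%, 24%, 16%, 10% and 5% at final levels of 0.10, 0.20, 0.30, 0.50 and 1.0 ng/mL. This rests on a linear rise, equal amounts per application, a limit of 0.05 ng/mL and a regression that meets the 50% condition.

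The documents do not support saying that the bias will occur or that it will be large. Near the assay limit it could roughly halve the slope; at 1 ng/mL it would hardly matter.

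**What to change.** **Laboratory tests.** Keep one rule: either exclude clinical laboratory parameters from the `<X` sentence in SAP 5.4, or delete the zero coding in Table 8.

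**Hypericin.** Exempt it from 5.4 and add to SAP 6.2:
- a pre-drug Baseline below the limit is set to 0;
- the number of samples below the limit is reported at each timepoint, alongside the median already planned;
- later values below the limit are analysed at 0 and at the assay limit as sensitivity bounds, including where before- and after-light samples are averaged. Left-censored regression is optional, given about 6 patients.

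The rule should cover undetected results however the laboratory records them, and the SAP should state the limit.

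**Cost.** A few sentences in the SAP and one extra run of the regression. No new data are needed.
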